9.4 Exploratory Bone Response Criteria

Quantitative Bone SPECT/CT Substudy to be performed at DFCI only.

Bone scans will be routinely performed as part of the radiologic evaluations for measurement of tumor response. SPECT/CT will be obtained at the time of each bone scan required per protocol as part of standard of care for anatomic localization of lesions. Methods to quantitate bone tracer are not as established as the standardized uptake value (SUV) is for FDG-PET/CT, but new methods and software are now available to perform quantitation on SPECT/CT (Cachovan et al. EJNMMI; 3:45, 2013). Additional processing and quantitative analysis with newer software will be performed as part of research to explore if and how quantitative changes in bone tracer uptake on SPECT/CT correlate with markers of bone turnover, immune biomarkers, response on standard

imaging (CT or MRI).

If SPECT/CT is unable to be completed at screening or at on study timepoints for logistical reasons, it will not be considered a protocol violation.

9.5 Mutations in DNA Repair Genes in Prostate Cancer (to be funded by Bayer)

Prostate cancer represents a broad clinical and biological spectrum ranging from indolent tumors to aggressive disease resulting in significant morbidity and mortality. Uncovering differences in the genetic makeup of tumors may improve our understanding of its clinical heterogeneity. Recent studies have helped define the molecular taxonomy of prostate cancer using comprehensive genomic analyses. Robinson et al. demonstrated the presence of a potential driver mutation in nearly all metastatic CRPC tumor samples which included frequent alterations in the AR (71.3%), PI3K (49%) and DNA damage repair (DDR) pathways (22.7%).²⁵

It is estimated that human cells encounter thousands of DNA damaging events on a daily basis.²⁶ These events can be mediated by endogenous (deamination and hydrolytic reactions, reactive oxygen species, DNA replication errors) and exogenous (ultraviolet light, ionizing radiation, alkylating agents and platinum compounds) sources.^{27,28} Depending on the causative agent, the extent of DNA damage can range from base modifications and nucleotide mismatch to double stranded DNA breaks which is the most biologically hazardous form of DNA damage.²⁹ In order to maintain genomic stability and compensate for these damaging events, cells have evolved several repair mechanisms such as base excision repair (BER), mismatch repair (MMR), nucleotide excision repair (NER) and double strand DNA repair pathways which includes homologous recombination (HR) and non-homologous end joining (NHEJ).³⁰ HR is the high fidelity mechanism preferentially used for repair of double strand DNA breaks and is mediated by proteins coded by genes such as BRCA-1, BRCA-2 and Rad52. The importance of these genes in maintaining genomic stability is highlighted by the high risk of familial breast and ovarian carcinoma and even some prostate cancers associated with germline BRCA-1 and BRCA-2 mutations (loss of function of these genes).

In addition to inherited germline mutations, these aberrations can be acquired through somatic changes. In advanced prostate cancer, germline and somatic mutations in DNA repair mechanisms have been reported in 11.8% and 22.7% of patients respectively.^{25,31} In recent study by Annala et al, the presence of DDR mutations was associated with a shorter time to the emergence of castration resistance (11.8 months vs. 19.0 months; P=0.03) and an attenuated response to AR targeted therapy in castration resistant setting.³² However, the presence of impaired DNA repair mechanisms also provides a therapeutic opportunity by targeting the inherent genomic instability of these tumor cells. Exploiting the biological principle of "synthetic lethality", the use of PARP inhibitors has been associated with impressive responses in patients with advanced ovarian cancer with somatic or germline BRCA mutations.³³ Mateo et al recently demonstrated the presence of somatic or germline alterations in DDR alterations in 33% of patients with CRPC who were treated with the PARP inhibitor olaparib in a phase 2 study and that it highly

correlated with response.³⁴ Response rates were 33% in the overall study population compared to 88% in the cohort with DNA repair alterations, thus suggesting the potential role of these abnormalities as predictive biomarkers of response. The impact of these mutations on the efficacy of radium-223, which induces double stranded DNA breaks and tumor cell death through alpha particles, is unknown.

We hypothesize that tumor cells with germline or somatic mutations in DDR genes will be more susceptible to the DNA damaging effects of radium-223. Supporting this hypothesis, Steinberger et al recently reported a durable response with 2 courses of radium-223 in a patient with a frameshift mutation in BRCA-2.³⁵ Further, the presence of impaired DNA repair pathways in the tumor cells has been associated with higher tumor mutational load, neo-antigen expression and response to immune checkpoint blockade across several solid tumors.³⁶⁻³⁸ Through this proposed correlative work, we aim to utilize whole exome sequencing (WES) to assess the impact of DNA repair and other genomic alterations on the clinical efficacy of radium-223 with or without the immune checkpoint inhibitor pembrolizumab.

Whole exome and transcriptome sequencing of tumor samples

Pre-treatment and on therapy biopsy specimens with matched germline samples will be used for whole exome and transcriptome sequencing in collaboration with the [name] Laboratory and the Center for Cancer Precision Medicine. Baseline alterations will be correlated with clinical outcomes. Induction of on-therapy changes will be characterized and correlated with efficacy. To be eligible for DNA isolation, tissue must contain at least 20% tumor nuclei. The DNA is then analyzed by massively parallel sequencing using a solution-phase Illumina hybrid capture kit and an Illumina HiSeq 2500 sequencer at the Broad Institute using established methodology. In parallel, capture based whole transcriptome sequencing, which can be performed from either frozen or formalin-fixed samples will be done on all tumor samples to determine gene expression quantification through orthogonal methods, as well as identify fusion products and alternative splicing events. Furthermore, RNA analysis through whole transcriptome sequencing will enable quantification of immune cell compartments that may be related to specific DNA repair mutations (e.g. mismatch repair) and may impact predictions of response, and this analysis can enable enrichment of likely pathogenic DNA repair mutations by distinguishing those that are present in DNA and also expressed in the RNA.

Circulating tumor derived cf-DNA in advanced prostate cancer

Genomic information derived from tissue based next generation sequencing is being increasingly employed in the clinic to guide treatment decisions. While it is an important step towards personalized medicine, there are limitations to tissue based sequencing assays. There can be significant genomic heterogeneity between the primary tumor and the metastatic sites.³⁹ As such, a biopsy of a single disease site might not be representative of the overall tumor clone. Further, genomic characteristics of tumors may change over the course of treatment with emergence of different resistant mechanisms.⁴⁰⁻⁴² Although biopsy of a metastatic site can provide genetic information at a given stage in

the disease course, it cannot provide insight into how subsequent therapies may induce clonal evolution or intrinsic dynamic changes in the biology of the tumor. While serial biopsies might accomplish this objective, they subject patients to repeated discomfort and increased risk of potential complications adding to the overall morbidity and anxiety of the disease.

Analyzing tumor derived cf-DNA in the blood can potentially circumvent the above challenges. cf-DNA is composed of fragments of coding and non-coding DNA which are released into the circulation during tumor cell apoptosis or necrosis.43 Previous studies have shown that compared to normal controls, patients with prostate cancer have significantly higher levels of cf-DNA.⁴⁴ High pretreatment levels of tumor derived cf-DNA have been associated with poor response to taxane chemotherapy and worse clinical outcomes.⁴⁵ In addition to quantitative changes, cf-DNA has the potential to establish pretreatment mutational signatures that may predict resistance or sensitivity to established and investigational therapies. Supporting this concept, Salvi et al demonstrated that pretreatment copy number gain in AR and CYP17A1 genes detected in cf-DNA samples was predictive of poor overall survival and progression-free survival (PFS).⁴⁶ Further, by comparing the genomic alterations at baseline, on treatment, and at the time of disease progression, it may be possible to uncover novel mutations, copy number alterations and somatic variants which can be acquired as a result of clonal evolution and lead to treatment failure.^{47,48} A major advantage of cf-DNA is that the sample is obtained by a simple blood draw and does not require a more invasive tumor biopsy.

Whole genome sequencing of circulating tumor derived cell free DNA

Blood samples will be obtained from patients enrolled in both arms prior to treatment initiation (week 1), on therapy at week 5 and week 13, and at the time of disease progression. Whole genome sequencing will be performed at 0.1x coverage, which we term ultra-low pass whole genome sequencing (ULPWGS). The sequencing information derived from ULPWGS will be used to estimate "tumor purity", which is defined as percent of circulating DNA derived from tumor cells in the blood, and to identify copy number alterations in the tumor using an adaptation of a probabilistic model, called ichorCNA.⁴⁹ While other algorithms for assessing copy number changes from cf-DNA have been described,^{50,51} ichorCNA has the advantage of accounting for mixtures of cell populations to assess for subclonal events and estimating tumor purity.

As this study was added during study enrollment, not all patients will have cfDNA analysis performed. Lack of cfDNA samples will not be considered a deviation.

The cfDNA samples will be analyzed by investigators at collaborating institutions, such as the Broad Institute, for patients enrolled on this trial. From these samples, the data will be submitted to the National Institutes of Health's Database for Genotypes and Phenotypes (dbGaP) and other public databases. Samples and data will be de-identified.

Details regarding obtaining and processing cfDNA can be found in the Laboratory Manual.

10. STUDY CALENDAR

All baseline evaluations are to be conducted within 42 days prior to treatment initiation.

Assessments must be performed prior to administration of any study agent. On-study assessments should be administered within 72 hours of the protocol-specified date but prior to study drug administration. Imaging assessments may have a window of +/- 7 days but must remain on schedule even if doses are being held for toxicity or other reasons.

For participants on Arm A, if pembrolizumab is discontinued for toxicity, visits and assessments will then follow the schedule for Arm B. If radium-223 is discontinued, visits and assessments will be every 3 weeks at the time of the pembrolizumab dosing. The radium-223 visits on Arm A will be discontinued and not considered a protocol violation. The quality of life questionnaires and immune studies will be done on the pembrolizumab visit closest to their required visit if they had stayed on radium-223 (e.g., will be done on week 7 instead of week 8). Imaging assessments will remain the same on an every 12 week basis.

Study Calendar	Pre- Study ^A	Wk 1	Wk 4 (Arm A only)	Wk 5	Wk 7 (Arm A only)	Wk 8	Wk 9	Wk 10 (Arm A only)	Wk 13+ (R)	End of Treatment ^S
Informed consent	Х									
Demographics	Х									
Medical history	Х									
Concurrent meds	Х	Х	Х	Х	Х	Х	Х	Х	Х	
Physical exam ^B	Х	Х	Х	Х	Х		Х	Х	Х	Х
Vital signs ^C	Х	Х	Х	Х	Х		Х	х	Х	Х
Height	Х									
Weight	Х	Х	Х	Х	Х		Х	х	Х	Х
ECOG Performance status	Х	Х	Х	Х	Х		Х	Х	Х	Х
CBC w/diff, plts ^D	Х	Х	Х	Х	Х		Х	Х	Х	Х
Serum chemistry ^E	Х	Х	Х	Х	Х		Х	Х	Х	Х
Testosterone	Х									
PSA ^F	Х	XF		Х			Х		Х	Х
TSH, Free T4 ^G	Х		х	Х					х	
PT/INR, PTT ^H	Х									
EKG	Х									
Pembrolizumab ^I (Arm A only)		х	Х		Х			х	Х	
Radium-223 ^J		Х		Х			Х		$(X)^{J}$	
Adverse event evaluation ^K		Х	х	Х	х		Х		х	Х
Radiologic evaluation & Tumor measurements ^L	X								X^L	
Correlative immune studies ^M		Х		Х			Х		X*	
Bone biopsy ^N	Х					Х				
cfDNA ⁰		Х		Х					Х	
FACT-P Survey ^P		Х		Х			Х		Xo	X
Brief Pain Inventory ^P		Х		Х			Х		Xo	Х
Analgesic Diary ^P		Х		Х			Х		Xo	Х
Follow-up ^Q										XQ

A: All baseline evaluations are to be conducted within 42 days prior to treatment initiation. In the event that the participant's condition is deteriorating, laboratory evaluations should be repeated within 48 hours prior to initiation of the next cycle of therapy. D1 labs and assessments do not need to be performed if have been done within 72hrs prior to study drug dosing. C1D1 labs do not need to re-meet eligibility criteria but do need to meet criteria as detailed in Section 5.2.1.

B: Physical examination should include general description of participant, head, eyes, and throat, chest, abdominal, extremities, neurologic, skin, and lymph node examination. Any other evaluation is up to the discretion of the practitioner. It will not be considered a violation if the exam is not described as outlined here. Patient will be seen in clinic the day of any study drug infusion (e.g., radium-223 and/or pembrolizumab)

C: Vital signs included blood pressure, heart rate, respiratory rate, body temperature

D: CBC with differential should be done before each dose of radium-223 and pembrolizumab.

E: Serum chemistry to include full CMP with sodium, potassium, chloride, bicarbonate, BUN, creatinine, glucose, calcium, albumin. Liver function tests to include AST, ALT, total bilirubin and direct bilirubin, alkaline phosphatase.

F: PSAs should be done at baseline, week 1 day 1 (per treating investigator's discretion), every 4-6 weeks on therapy, and at study end.

G: TSH, Free T4 to be done a baseline, week 4 (week 5 for arm B), week 13, and then approximately every 12 weeks.

H: Coagulation factors to include PT and INR.

I: Pembrolizumab will be given by IV every 3 weeks (+/- 3 days) in Arm A only.

J: Radium-223 will be given by IV every 4 (+/- 7 days) weeks for a maximum of 6 doses.

Arm A: Radium-223 will be held after 3 doses. It may be restarted (to complete the final doses up to a maximum of 6 from study start) when there is progressive disease in bones as long as there is no new visceral disease.

Arm B: Radium-223 will be given as per standard of care monthly for 6 months in a row without breaks except for toxicity/intolerance as detailed in Section 6.2.

K: Adverse events will be monitored continuously

L: Diagnostic CT chest and CT or MRI of the abdomen and pelvis and bone scan including SPECT/CT should be obtained at baseline and every 12 weeks (+/- 7 days). (NOTE: SPECT/CT will be done only at DFCI.) Scans should remain on an every 12 week schedule (+/- 7 days) even if dose delays occur.

M*: Correlative immune studies: will be obtained and transported overnight at room temperature to the [name] Lab at UCSF. Samples for immune studies will be done at week 1 (pre-dose), week 5, week 9, week 13, week 21 and at the time of progression for those patients still on study.

N: Bone biopsy: archival tissue is permitted for baseline analysis. IR guided bone biopsy will be done at week 8 (+3 weeks) after the second dose of radium-223. If the second dose cannot be given for safety reasons, biopsy should still be performed within the window detailed here.

O: Blood samples for cell free DNA (cf-DNA) will be performed at treatment initiation (week 1, pre-dose), on treatment (week 5 and 13), and at time of progression.

P: Quality of life, pain and analgesic use will be measured via the FACT-P (Appendix B), Brief Pain Inventory (Short Form) (Appendix C), and analgesic diary (Appendix D) prior to treatment, at week 5, 9, then every 6-8 weeks after week 9 (as schedules differ between the two arms), and at treatment progression/off study visit.

Q: After progression/treatment discontinuation, follow the participant for survival, receipt of next line therapies, and post-treatment SSEs every 6 months until death or 2 years after treatment discontinuation.

R: Arm A study assessments will continue based on the same schedule as detailed for weeks 1-13 when pembrolizumab is given alone (e.g., visits, labs, assessments every 3 weeks only). If radium-223 is resumed upon progression, assessment schedule and radium-223 + pembrolizumab dosing will resume based on the schedule detailed for weeks 1-13. Arm B study assessments and radium-223 dosing will continue based on the same schedule detailed for weeks 1-13 up to 6 doses without breaks except for toxicity/intolerance (Section 6.2).

Note: For both arms: Immune studies will follow the schedule detailed in footnote M*

S: End of Treatment visit should occur within 30 days after last study treatment.

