nonsteroidal antiandrogens). Screening may commence during this washout window.

- Any patient who has not recovered (i.e., ≤ Grade 1 or at baseline) from adverse events or complications due to a previously administered systemic agent, radiation therapy, or major surgery.
 - Exceptions:
 - Subjects with ≤ Grade 2 neuropathy, hot flashes, or hypertension may qualify for the study if all other eligibility criteria met.
 - Other toxicity or complications that are deemed by the treating investigator as not clinically significant (e.g., urinary incontinence from past prostatectomy, peripheral edema from past taxane therapy)
- Diethylstilbestrol, estrogens, saw palmetto, or other preparations that are known to have possible endocrine effects on prostate cancer that have been started within the past 8 weeks, as they may affect PSA levels or response. These are allowed if the patient has been on a stable dose for at least 8 weeks prior to C1D1.
- Receiving other investigational agents
- History of allergic reactions to compounds with similar biologic or chemical composition to pembrolizumab or radium-223
- Has a known additional malignancy that is progressing or requires active treatment. Exceptions include basal cell carcinoma of the skin or squamous cell carcinoma of the skin that is planned for curative therapy.
- Has known active central nervous system (CNS) metastases and/or carcinomatous meningitis. Subjects with previously treated brain metastases may participate provided they are stable (without evidence of progression by imaging for at least four weeks prior to the first dose of trial treatment and any neurologic symptoms have returned to baseline), have no evidence of new or enlarging brain metastases, and are not using steroids for at least 7 days prior to trial treatment. This exception does not include carcinomatous meningitis, which is excluded regardless of clinical stability.
- Has active autoimmune disease that has required systemic treatment in the past 2 years (i.e. with use of disease modifying agents, corticosteroids or immunosuppressive drugs). Replacement therapy (e.g., thyroxine, insulin, or physiologic corticosteroid replacement therapy for adrenal or pituitary insufficiency, etc.) is not considered a form of systemic treatment and is allowed.
- Has known history of, or any evidence of active, non-infectious pneumonitis. A history of radiation pneumonitis which is asymptomatic with no signs of active process is allowed.

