*Lupron/GnRH agonist or antagonist should be continued unless intolerable or discontinued for other safety reasons.

**Adhering to the schedule should be encouraged, and the 7 day window should not be utilized to give pembrolizumab and radium-223 on the same day for scheduling convenience.

Order of Administration – In the combination arm, pembrolizumab should be administered prior to radium-223 on days when both are given on the same day. No minimum time is required between the administration of drugs.

Table 4: ARM B - Control Arm

Agent	Premedication	Dose	Route	Schedule
Radium-223	None	55kBq/kg	IV over 1 minute	Every 4
		(1.49µCi)/kg	or longer per	weeks (28
			institutional	+/- 7 days)
			standards	for 6 doses

*Lupron/GnRH agonist or antagonist should be continued unless intolerable or discontinued for other safety reasons.

Trial treatment should begin on the day of randomization or within 7 days after randomization.

The Pharmacy Manual contains specific instructions for the preparation of the pembrolizumab infusion fluid and administration of infusion solution (Section 8.1).

5.2 **Pre-Treatment Criteria**

5.2.1 Cycle 1, Day 1

Pre-Treatment Criteria for C1D1. D1 dosing criteria of subsequent cycles (2 and beyond) should follow Section 6 guidelines:

C1D1 labs must meet the following criteria prior to treatment but do not need to re-meet eligibility criteria:

- Absolute neutrophil count \geq 1,500/mcL
- Hemoglobin ≥10g/dL *transfusions and/or erythropoietin supplementation permitted
- Platelets $\geq 100,000/mcL$
- Total bilirubin ≤1.5x institution's upper limit of normal (unless known Gilbert's syndrome)
- AST(SGOT)/ALT(SGPT) $\leq 2.5 \times$ institutional upper limit of normal ULN
- Creatinine clearance ≥30 mL/min/1.73 m² for participants with creatinine levels above institutional ULN. (*Note: creatinine clearance should be calculated per institutional standard*)
- If screening assessments have been done within 72 hrs prior to C1D1, they may be used in lieu of repeat C1D1 assessments (e.g., labs, ECOG, exam).

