11.1.9 Methods for Evaluation of Changes in PSA

Biochemical Response:53

The laboratory will utilize a consistent method to check serum PSA at baseline, every other cycle while on treatment, and at study termination.

PSA decline \geq 50% from baseline to 12 weeks of therapy and which has been confirmed with a second PSA at \geq 3 weeks later.

Percent change in serum PSA:²³

The percent change (rise or fall) from baseline at 12 weeks, and separately, the maximal change (rise or fall) at any time will be recorded using a waterfall plot.

PSA Progression:

PSA progression is defined as $\geq 25\%$ increase and ≥ 2 ng/mL increase above the nadir or baseline value for patients who had a PSA decrease on treatment which is confirmed by a second value 3 or more weeks later.

For patients without a decrease on treatment, PSA progression is defined as $\geq 25\%$ and a $\geq 2 \text{ ng/mL}$ after 12 weeks.

PSA progression must be confirmed at the next study visit 4 weeks later.

PSA progression alone will not be considered diagnostic of disease progression, and will not be used as a reason to discontinue study treatment.

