13. STATISTICAL CONSIDERATIONS

13.1 Study Design/Endpoints

This is an open label phase 2 trial that randomizes 45 mCRPC patients (2:1 ratio) to radium-223 plus pembrolizumab combination therapy or to radium-223 monotherapy. The primary objective is to compare the increase in immune CD8+ and CD4+ T cell infiltration levels from baseline to 8 weeks on treatment between the two treatment arms.

Primary Endpoint:

Difference in tissue immune cell (e.g., CD4+/8+T) infiltration in the bone metastasis biopsy specimens from baseline to 8 weeks on treatments in both the combination and monotherapy arms.

Secondary Endpoints:

- Safety and Tolerability: grade 3 or higher adverse events that are considered treatment related according to NCI CTCAE (version 4.0)
- Progression-free survival (PFS): is defined as the time from the first dose of study drug to the earlier of the first documentation of definitive disease progression [as

defined by Response Evaluation Criteria in Solid Tumors (RECIST version 1.1) and PCWG2] or death due to any cause. Participants alive without disease progression are censored at date of last disease evaluation

• Overall survival as defined in 11.1.8

Exploratory Endpoints:

- Clinical-based endpoints
 - Changes in PSA
 - PSA response: defined as decline ≥50% from baseline to 12 weeks of therapy and which has been confirmed with a second PSA at ≥ 3 weeks later
 - Time to PSA progression as defined in 11.1.9
 - Time to normalization of alkaline phosphatase (if initially elevated)
 - Time to decrease in alkaline phosphatase (if initially elevated)
 - Symptomatic skeletal events (SSEs): Rate of SSEs and time to first SSE
 - Changes in osteoblastic activity on bone scan (assessed using the quantitative SPECT/CT)
 - Changes in quality of life, pain, and analgesic use, and time to introduction of analgesics
 - Immune-based endpoints
 - Quantify the CD8, CD4, and FoxP3+ CD4 (Treg) cell infiltration in the bone biopsy specimens, and to subsequently quantify the CD8/Treg and CD4/Treg ratios
 - Change in circulating T cell clonality
 - Induction of IgG antibody response
 - Changes in PD-L1 expression and co-regulation of other immune checkpoints such as TIM-3, LAG-3, and PD-L2
 - Changes in immunosuppressive cell populations and cytokines (e.g., MDSCs, Tregs, TGF-β, and iNOS)
 - Change in serum chemokines: (e.g., CXCL9, CXCL10)

- Changes in soluble PD-L1 ([name] Lab assay)
- Genomic-based endpoints

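### The only required pre-treatment PSA may be 42 days old and no rule says which value is baseline, so change before the first dose is counted as on-treatment change in the exploratory PSA endpoints

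*Combined protocol and SAP*

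**What the plan says.** The PSA schedule is in footnote F of the Study Calendar (Section 10): "PSAs should be done at baseline, week 1 day 1 (per treating investigator's discretion), every 4-6 weeks on therapy, and at study end". Footnote A sets the age limit for pre-study tests: "All baseline evaluations are to be conducted within 42 days prior to treatment initiation". Section 3.3 adds, of the two-week washout from earlier prostate cancer therapy, "Screening may commence during this washout window", so the pre-study PSA may be drawn before that washout is complete.

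Nothing else makes a Week 1 PSA compulsory. Section 5.2.1 says "C1D1 labs must meet the following criteria prior to treatment but do not need to re-meet eligibility criteria", and its list covers blood counts, liver tests and creatinine clearance but not PSA. Footnote A waives Day 1 tests when recent ones exist ("D1 labs and assessments do not need to be performed if have been done within 72hrs prior to study drug dosing"). That sets a 72-hour window without turning an optional PSA into a required one.

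The endpoints depend on a baseline. Section 13.1 has "PSA response: defined as decline ≥50% from baseline to 12 weeks of therapy", with confirmation at least 3 weeks later. Section 11.1.9 adds percent change at 12 weeks, maximal change, and PSA progression. For patients with a decrease on treatment, progression is a rise of at least 25% and at least 2 ng/mL above the nadir or baseline. For patients without a decrease, the same amounts apply after 12 weeks, but no reference value is named. No section says which draw is baseline, even when a patient has both a pre-study and a Week 1 value.

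The on-treatment rules also differ. Footnote F has a draw every 4 to 6 weeks; Section 11.1.9 has "every other cycle while on treatment, and at study termination". Section 11.1.9 first asks for confirmation at 3 weeks or later, then says "PSA progression must be confirmed at the next study visit 4 weeks later".

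**The concern.** A change-from-baseline endpoint measures treatment only if the baseline is taken close to the first dose. Here up to six weeks can separate the two, and any PSA movement in that gap becomes part of the recorded on-treatment change. The 50% response rate, the 12-week and maximal percent changes, and the progression rule for patients without a decrease are all exposed.

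PSA is also the exception within its own calendar. Footnotes M and O fix the immune and cell-free DNA samples at Week 1 before dosing, and CBC and chemistry are drawn at that visit. PSA response is used again in the DNA-repair analyses (Sections 13.1 and 13.11), and PSA change is compared between arms by a Wilcoxon rank sum test (Section 13.9). An avoidable error in the reference value carries into all of these.

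**Working it through.** The plan states no expected PSA rate, power or doubling time, so there is no figure to reproduce. The check asks how far a 42-day-old baseline can move the recorded result.

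**Inputs from the documents:** maximum baseline age 42 days (Sections 3.1 and 10); response threshold 50% and progression thresholds 25% and 2 ng/mL (Sections 11.1.9 and 13.1); 72-hour window (footnote A).

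**Assumption:** exponential PSA growth before the first dose with doubling time DT, shown from 2 to 12 months (1 month = 30.44 days). The documents give no DT.

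**Step 1: drift.** Let g be the Day 1 PSA divided by the baseline PSA: g = 2^(42/DT). At 2 months, DT = 60.9 days, 42/60.9 = 0.690, and g = 2^0.690 = 1.61.

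**Step 2: response.** A true 50% fall from Day 1 is recorded as a change of 0.5g − 1. The true fall needed to record 50% is 1 − 0.5/g. At 2 months these are 0.5 × 1.613 − 1 = −0.19 and 1 − 0.5/1.613 = 0.69.

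| Assumed DT | g | True 50% fall is recorded as a fall of | True fall needed to record 50% |
|---|---|---|---|
| 2 months | 1.61 | 19% | 69% |
| 4 months | 1.27 | 37% | 61% |
| 6 months | 1.17 | 41% | 57% |
| 12 months | 1.08 | 46% | 54% |

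If PSA falls before Day 1, g is below 1 and the error reverses: a true fall of less than 50% is recorded as a response.

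**Step 3: progression without a decrease**, taking the pre-study value as the unnamed reference. Pre-dose growth alone reaches 25% when DT ≤ age × ln 2 / ln 1.25. For 42 days this is 42 × 0.693/0.223 = 130 days (4.3 months). For a 28-day-old baseline it is 87 days (2.9 months), and for 14 days it is 43 days (1.4 months). The 2 ng/mL condition needs a baseline PSA of at least 2/(g − 1): 3.3 ng/mL at a DT of 2 months, 7.4 ng/mL at 4 months. The rise must still be present after week 12 and be confirmed.

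With unchanged growth, a Day 1 baseline shows +25% by day 84 if DT ≤ 84 × 0.693/0.223 = 261 days (8.6 months). A 42-day-old baseline shows it if DT ≤ 126 × 0.693/0.223 = 391 days (12.9 months). Between those two values, only the age of the baseline puts the patient over the threshold by day 84.

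**Step 4: after the fix.** With a baseline 3 days old, g = 2^(3/DT) is 1.035 at 2 months and 1.006 at 12 months. The true fall needed is 51.7% and 50.3%. Pre-dose growth alone would reach 25% only if DT were about 9 days or less (3 × 0.693/0.223 = 9.3).

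**Step 5: sampling rules side by side.** Section 5.1 says treatment is counted in weeks rather than cycles because the two drugs have different intervals, so sampling by cycle has no fixed length here, although Section 5.2 and footnote A still use cycle labels. A value 4 weeks later satisfies a rule of 3 weeks or more, so the two confirmation rules can both be met. They part company in Arm A on pembrolizumab alone, where visits are every 3 weeks (footnote R) and the next visit is not 4 weeks later.

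**The case against.** The strongest reply is that footnote F lists baseline and Week 1 as separate time points and the calendar has a pre-study PSA column. The plainest reading makes the mandatory pre-study draw the baseline for everyone. The optional draw then changes no endpoint, and randomization balances baseline age between arms on average. That reading is reasonable, but it leaves the error in Steps 1 to 3 in place, and the plan never states it.

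Three stronger readings may tempt a reader; the documents do not support them.

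- *PSA response is always understated.* This requires PSA to rise before Day 1. Section 3.2 admits patients on PSA rise or bone progression, screening may overlap washout, and no pre-dose trend is given. The error can run either way.
- *Progression can be reached before the first dose.* Without a decrease, Section 11.1.9 counts progression only after 12 weeks, with the 2 ng/mL rise and confirmation. With a decrease, an on-treatment nadir used as reference does not depend on baseline age.
- *Investigators who know the arm bias the comparison.* The trial is open label and treatment starts 0 to 7 days after randomization, so the arm can be known when the draw is decided. Bias follows only if Week 1 values replace the pre-study value, and no such rule is written.

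It also stands that 42 days is a maximum, that actual ages are unknown, and that the endpoints are exploratory and without stated power.

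**Conclusion.** The point holds as a cheap improvement. The required pre-treatment PSA may be 42 days old, the Week 1 PSA is discretionary, and baseline is undefined. The size depends on the assumed doubling time and on baseline age: at the full 42 days the true fall needed to record a response runs from 54% (12 months) to 69% (2 months), and a fresher baseline shrinks the error. For patients scored as having no decrease, pre-dose growth can contribute to the 25% rise and, at doubling times of about 130 days or less with a 42-day-old baseline, supply it alone, subject to the 12-week, 2 ng/mL and confirmation conditions.

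If the pre-study value is used throughout, the result is within-arm distortion and added noise. Arm-dependent bias is possible only if discretionary Week 1 values serve as baseline. The primary endpoint, PFS and OS are untouched, and Section 11.1.9 says PSA progression alone neither defines disease progression nor stops study treatment.

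**What to change.** - Footnote F: require a pre-dose Week 1 PSA, taken within 72 hours before the first dose.
- Sections 11.1.9 and 13.1: define baseline for all PSA endpoints as the last PSA before the first dose. For patients already treated without a Week 1 draw, report the age of that value. This matters because Section 9.5 shows that enrolment had begun before this version; a baseline restricted to Week 1 would leave such patients with none.
- Section 11.1.9: name that baseline as the reference for patients without a decrease, replace sampling by cycle with the calendar schedule, and keep one confirmation rule, a value 3 or more weeks later, which visits in both arms can meet.

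The cost is one extra PSA tube at a visit that already draws blood, plus amendment wording.
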